15.4 Analysis of Secondary and Tertiary Endpoints

The key secondary endpoint will be analyzed for time-to-event endpoints, using the Cox regression model for survival data will be used to test the statistical significance of differences in mortality between the treatments. Kaplan-Meier curves will be generated to graphically display the mortality rates as a function of time from randomization in each treatment. Patients will be censored when upgraded to a status 1-3, at the time of transplant, transfer of care to another LVAD center, device decommissioning or explant for myocardial recovery.

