4 OBJECTIVES AND ENDPOINTS

4.1 Primary Objectives

The primary objective is to evaluate the safety of apixaban as compared to warfarin in LVAD patients.

Hypothesis: In patients with a HM3 LVAD, treatment with apixaban for 24 weeks will be non-inferior with respect to freedom from death or hemocompatibility related adverse events (stroke, device thrombosis, bleeding, aortic root thrombus, and arterial non-CNS thromboembolism), compared to treatment with warfarin.

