7.3 Study Intervention Phase

Study treatment will be using the target dose of apixaban 5mg po BID or warfarin po daily for a goal INR of 2.0 to 2.5. All patients will be treated with aspirin 81mg daily as per the IFU. Randomized participants will receive the first dose of study drug as follows:

- LVAD patients randomized to warfarin will begin treatment once all anticipated surgical procedures are complete and the patient is deemed stable for transfer out of the ICU. Warfarin will be overlapped with low intensity heparin until the INR is at least 2.0. Warfarin will be dosed to maintain an INR goal of 2.0-2.5. For ambulatory LVAD patients, warfarin therapy will be continued.
- LVAD patients randomized to apixaban will transition from heparin to apixaban once all anticipated surgical procedures are complete and the patient is deemed stable for transfer out of the ICU. Heparin will be discontinued at the same time apixaban is initiated. For ambulatory LVAD patients on warfarin, warfarin will be transitioned to apixaban when the INR < 2.0.

Dose adjustments of apixaban will not occur. Dose adjustments of warfarin will be made no less than every 4 weeks to achieve the goal INR of 2.0 to 2.5. Participants will return to clinic according to the schedule shown in Appendix C.

For patients upgraded on the transplant list from a status 4 or below to a status 1-3, apixaban will be transitioned to warfarin, to allow for drug reversal at time of transplant. Patients randomized to the apixaban arm will be replaced to ensure 20 LVAD patients are exposed to apixaban over the duration of the study. Warfarin patients will not be replaced, as warfarin is standard of care therapy for LVAD patients.

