14.1.8 Subject Stopping Criteria and Drug Modification

For patients in the apixaban arm with a thromboembolic event (stroke, device thrombosis or arterial non-CNS thromboembolism), will be considered a study drug failure and converted to warfarin (withdrawn from active treatment). For patients experiencing a bleeding event, the aspirin will be discontinued. Only in patients with recurrent bleeding will the apixaban be discontinued (withdrawn from active treatment) and warfarin initiated at an INR goal of 1.5 to 2.0. Patients will continue to be followed per the study schedule through study completion.

For apixaban patients listed for transplant, who are upgraded to a status 1-3, the apixaban will be discontinued and the patient converted to warfarin. These patients will be followed until transplant or study completion. Each apixaban patient who does not complete the 6-month study duration will be replaced to ensure 20 patients are in the apixaban arm with complete follow-up.

For patients in the warfarin arm with a thromboembolic event, will be managed with a higher INR goal of 2.5 to 3.0. For patients experiencing a bleeding event, the aspirin will be discontinued. Only in patients with recurrent bleeding will the INR goal range be reduced to 1.5 to 2.0. For patients with a 3rd bleeding event, warfarin will be stopped, and the patient will be withdrawn from treatment and the patient followed according to the study protocol.

Any AE events occurring up to 72 hours after the study drug is discontinued will be considered a treatment-emergent adverse event.

All SAEs, except for those anticipated events listed above, occurring from signed informed consent through study completion will be captured on the AE eCRF. Unless exempted as described above, all SAEs, whether or not deemed drug-related or expected, must be reported to the IRB by the investigator or qualified designee within 24 hours of first becoming aware of the event. For this study, all-cause deaths will be reported on the AE eCRF. The investigator or qualified designee will enter the required information regarding the SAE into the appropriate module of the eCRF. If the eCRF system is temporarily unavailable, the event, including the investigator-determined causality to study drug should be reported via the back-up paper AE form. Upon return of the availability of the electronic data capture (EDC) system, the SAE information must be entered into the eCRF.

Follow-up

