15 STATISTICAL METHODS AND DATA ANALYSIS

15.1 General Design Issues

All planned analyses will be prospectively defined for this study and approved by the CC. The statistical analysis plan (SAP) will contain detailed information regarding the data analysis. The SAP will be finalized prior to trial completion and will be approved by the coordinating center statistical team.

Analysis of the DOAC LVAD Study will be based on intention to treat (ITT). That is, participants will be analyzed (and endpoints attributed) according to the treatment strategy to which participants are randomized, regardless of subsequent additional post-randomization treatment and medical care. The ITT population will correspond to all randomized participants. The primary and secondary analyses will follow the ITT principle.

Baseline demographic and clinical variables will be summarized for each randomized arm of the study. Descriptive summaries of the distribution of continuous variables will be presented in terms of percentiles (e.g., median, 25th and 75th percentiles) along with means and standard deviations. Categorical variables will be summarized in terms of frequencies and percentages.

In addition, exploratory analyses will be performed to help explain and understand findings observed from the planned analyses. Statistical tests with a p-value <0.05 will be considered statistically significant, unless otherwise stated. Analyses will be performed using SAS software (SAS Institute, Inc, Cary, NC).

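### Section 15.4 censors patients at upgrade to transplant status 1-3, against the ITT rule in 15.1, so deaths recorded after upgrade drop out of the mortality analysis

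*Combined protocol and SAP*

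**What the plan says.** Section 15.1 (General Design Issues) attributes endpoints to the randomized strategy "regardless of subsequent additional post-randomization treatment and medical care" and adds: "The primary and secondary analyses will follow the ITT principle". All-cause mortality is a listed secondary endpoint (section 12.2).

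Section 15.4 sets out a Cox model and Kaplan-Meier curves for mortality and then says: "Patients will be censored when upgraded to a status 1-3, at the time of transplant, transfer of care to another LVAD center". Device decommissioning and explant for recovery complete the list. Section 15.3, on the primary composite, gives no censoring rule.

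Section 7.3 says what upgrade means for treatment: "For patients upgraded on the transplant list from a status 4 or below to a status 1-3, apixaban will be transitioned to warfarin". Section 14.1.8 repeats the switch and says of these patients: "These patients will be followed until transplant or study completion". The same section captures SAEs (apart from the listed anticipated events) from consent to the end of the study and states: "For this study, all-cause deaths will be reported on the AE eCRF".

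**The concern.** Under 15.1, a change of treatment or care after randomization does not stop endpoints counting. Under 15.4, a change of listing status does, although in the apixaban arm its protocol consequence is a drug switch and in the warfarin arm there is no switch at all. Two analysts could each follow one section and report different mortality from the same data.

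Censoring is harmless only if patients censored at upgrade have the same later risk of death as those who remain. There is reason to doubt that here. Appendix B counts urgent transplant listing among the events that can accompany suspected device thrombosis, so a move up the list may follow a serious complication. The documents do not equate urgent listing with status 1-3, so this is a reason for suspicion and not proof. If upgrade does mark higher risk, the Cox and Kaplan-Meier results understate mortality, and section 15.2 says the data will inform the phase III design.

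**Working it through.** **Passages side by side**

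| Question | Section 15.1 | Section 14.1.8 | Section 15.4 |
|---|---|---|---|
| Does upgrade end follow-up? | Not addressed | No, for apixaban patients: followed to transplant or study end | Not addressed |
| Is a death after upgrade recorded? | Not addressed | Yes: all deaths go on the AE eCRF, with no limit by arm | Not addressed |
| Does it count in the mortality analysis? | Yes, by randomized arm | Not addressed | No, the patient is already censored |

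The exclusion of status 1-3 at entry and the listing checks at visits do not resolve this, because 14.1.8 continues follow-up after upgrade.

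**Size**

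The plan has no figure to reproduce: it gives no mortality, listing or upgrade rate, and 15.2 says the sample size was not statistically derived. All rates below are assumptions.

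Take 24 weeks (168 days) as the time unit.
- m = 24-week mortality at the pre-upgrade hazard; λ = -ln(1-m).
- u = 24-week probability of upgrade; γ = -ln(1-u).
- k = hazard after upgrade divided by hazard before; hazard after = kλ.
- τ = 168 / mean days from upgrade to transplant (0 if no transplant).

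Censoring at upgrade leaves only the pre-upgrade hazard, so Kaplan-Meier returns m. Keeping follow-up and censoring only at transplant gives:
- at risk, not upgraded: A(t) = exp(-(λ+γ)t)
- at risk, upgraded: B(t) = γ[exp(-(λ+γ)t) - exp(-(kλ+τ)t)] / (kλ+τ-λ-γ)
- risk = 1 - exp(-∫(λA + kλB)/(A+B) dt) over 0 to 1.

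Worked case: m = 0.10, u = 0.10, k = 3, no transplant. Then λ = γ = 0.1054.
- Deaths before upgrade: λ/(λ+γ) × (1 - 0.9 × 0.9) = 0.5 × 0.19 = 0.095.
- Deaths after upgrade: 0.095 - 0.9³ × (1/0.9 - 1) = 0.095 - 0.729 × 0.1111 = 0.014.
- Total 0.109 against 0.100 when censored at upgrade: understated by 0.9 points. Expected dropped deaths among 40 patients: 40 × 0.014 = 0.56. With transplant after a mean of 28 or 56 days, numerical integration gives 0.16 or 0.26.

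Understatement in percentage points (mean wait 28 days / 56 days / no transplant):

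| m | k | u = 5% | u = 10% | u = 20% |
|---|---|---|---|---|
| 10% | 3 | 0.13 / 0.21 / 0.45 | 0.27 / 0.43 / 0.90 | 0.57 / 0.91 / 1.83 |
| 10% | 6 | 0.31 / 0.50 / 1.01 | 0.65 / 1.02 / 2.04 | 1.36 / 2.13 / 4.14 |
| 5% | 3 | 0.07 / 0.11 / 0.24 | 0.14 / 0.23 / 0.48 | 0.30 / 0.48 / 0.98 |
| 5% | 6 | 0.17 / 0.27 / 0.56 | 0.34 / 0.55 / 1.14 | 0.73 / 1.16 / 2.32 |

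At k = 1 every entry is 0.

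For scale, the standard error of a 20-patient arm is √(0.10 × 0.90/20) = 6.7 points, or √(0.05 × 0.95/20) = 4.9 points. One death is 1/20 = 5.0 points. Section 14.1.8 says "Each apixaban patient who does not complete the 6-month study duration will be replaced"; if two are replaced and all randomized patients are analysed, one death is 1/22 = 4.5 points.

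**Effect of the remedy on the comparison**

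Let the apixaban hazard be 1.5 times the warfarin hazard before upgrade, with both arms at 3 times the warfarin hazard after it (10% warfarin mortality, 10% upgraded).
- Censored at upgrade: hazard ratio 1.50, risk difference (1 - 0.9^1.5) - 0.10 = 4.62 points.
- Follow-up kept: hazard ratio (ratio of cumulative hazards) 1.479 / 1.468 / 1.436, risk difference 4.54 / 4.50 / 4.37 points.
- Most extreme case run at this hazard ratio and mortality (20% upgraded, 6 times, no transplant): 1.319 and 4.07 points.

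**The case against.** **The follow-up sentence names apixaban patients only.** Listing checks at visits are described as confirming continued eligibility, which could be read as ending a warfarin patient's participation at upgrade. The wording is indeed less explicit for warfarin. But the SAE and all-cause death rules in 14.1.8 have no limit by arm, and section 18.4 encourages continued visits after treatment stops.

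**The edit is selective.** Strict ITT would also question censoring at transplant, transfer, decommissioning and explant. Transplant matches the point where 14.1.8 ends follow-up for upgraded apixaban patients. The other reasons could be examined too, but leaving them in place does not make this correction worse.

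**Censoring at the drug switch suits the hypothesis.** Section 4.1 states that "treatment with apixaban for 24 weeks will be non-inferior", and upgraded apixaban patients are no longer on apixaban. This is the strongest point. Yet no section declares an on-treatment analysis as the target, and 15.4 would not deliver one: patients converted to warfarin after a thromboembolic event or recurrent bleeding are not on its censoring list, while warfarin patients, who have no switch at upgrade, are censored. What stands is that the analysis censored at upgrade is informative and should be kept.

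**A fuller SAP is promised, and this is a pilot.** Section 15.1 does defer detail, but the conflict is already in the text from which that SAP will be written. Section 15.2 disclaims statistical significance and reviews each patient individually, and the deaths stay in the AE records. That limits the consequence to the model-based mortality results; it does not remove the contradiction.

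**Conclusion.** The concern holds. The plan's mortality analysis discards deaths that the plan itself collects, against its own ITT rule, and no passage reconciles the two. This conclusion rests on the text alone.

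The numerical size is modest and depends on assumed rates. With 5-20% upgraded and a 3- to 6-fold hazard after upgrade, mortality is understated by 0.1 to 2.1 points with transplant and 0.5 to 4.1 without, at 10% pre-upgrade mortality. At 5% the ranges are 0.1 to 1.2 and 0.2 to 2.3. All are below one standard error of an arm. There is no bias if upgrade carries no extra risk. In a trial this small the practical risk is a single omitted death, which visibly moves an arm's estimate. It should be corrected before the SAP is finalized. Whether the same censoring is meant for the primary composite cannot be told from 15.3.

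**What to change.** - In 15.4, remove upgrade to status 1-3 from the censoring list, so that deaths and events count by randomized arm to week 24 or to one of the remaining listed reasons.
- In 15.3, state the same rule for the primary analysis.
- Add the analysis censored at upgrade as a labelled sensitivity analysis for both.
- A sentence in 14.1.8 confirming that upgraded warfarin patients are followed in the same way would close the remaining ambiguity.

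The core change costs one phrase, one sentence and one line. It needs no new data collection and leaves clinical management at upgrade unchanged.

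The price is some dilution: events on warfarin after upgrade are attributed to apixaban, which can pull the arms together and so favours non-inferiority. In the base case above, a hazard ratio of 1.50 becomes 1.47 to 1.48 with transplant or 1.44 without. The sensitivity analysis shows the reader how far this matters.

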16 DATA MANAGEMENT PROCEDURES

16.1 Overview of Data Management

The CC will have primary responsibility for data management, including the development of data collection systems, data monitoring processes, and data storage and back-up. State-of-the-art technology will be used for the management of the network's data.

16.2 Data Security

Access to databases will be controlled centrally by the CC through user passwords linked to appropriate privileges. This protects the data from unauthorized changes and inadvertent loss or damage. Database and web servers will be secured by a firewall and through controlled physical access. Database back-up will be performed daily using standard procedures in place at the CC. All disk drives that provide network services, and all user computers, will be protected using virus-scanning software.

16.3 Publication Policy

Dissemination of preliminary information can adversely affect the objectivity of study data. For this reason, investigators will not be allowed to perform subset analyses at any point before the conclusion of the study, and any data, other than safety data, cannot be used for publication or reporting outside of this study until the study is completed or discontinued by the principal investigator.

17 STUDY ADMINISTRATION

17.1 Data and Safety Monitoring Board

An independent Data and Safety Monitoring Board (DSMB) has been convened to assess the progress of the clinical study, the safety data, and critical efficacy endpoints (if appropriate) and provide recommendations to the sponsor. The members of the DSMB serve in an individual capacity and provide their expertise, including recommendations regarding the continuation, modification, or termination of any or all arms of the study. The DSMB will review cumulative study data to evaluate safety, study conduct, scientific validity, and data integrity of the study. A separate DSMB charter outlines their roles and responsibilities.

17.2 Study Termination

The study may be terminated by the Sponsor at any time with suitable written notice to the reviewing IRB and applicable regulatory agencies. The study may be terminated by the DSMB based on concerns for significant harm to study participants based on criteria outlined in the DSMB charter. The following clinical events in the apixaban arm will result in an immediate pause of study enrollment for an evaluation by the independent DSMB:

- ≥ 2 thromboembolic events (ischemic stroke, arterial non-CNS embolism, device thrombosis, aortic root thrombus)
- ≥ 4 major bleeding events (Types 3-5)
- ≥ 2 deaths due to either thromboembolic events or major bleeding events

Patients who are already enrolled in the study will continue study-related activities during the enrollment pause.

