19.2 Appendix B - Adverse Event Definitions

- Arrhythmias: Any documented arrhythmia that results in clinical compromise, or requires hospitalization or treatment. Arrhythmias will be further classified as sustained ventricular arrhythmia or sustained supraventricular arrhythmia
- Arterial non-CNS thromboembolism: Acute systemic arterial perfusion deficit in any non-cerebrovascular organ system due to thromboembolism confirmed by 1 or more of the following: 1) standard clinical and laboratory testing, 2) operative findings, 3) autopsy findings
- Bleeding: the location/source of the bleed will be recorded and subsequently categorized as follows; CNS bleeding will be captured under cerebrovascular event/stroke
 - Type 2: Any overt, actionable sign of hemorrhage that does not fit the criteria for Type 3, 4, or 5 but does meet at least one of the following criteria:
 - 1) requiring non-surgical, medical intervention by a healthcare professional
 - 2) leading to hospitalization or increased level of care; or
 - 3) prompting evaluation
 - Type 3a
 - Overt bleeding accompanied by hemoglobin drop of 3 to < 5 g/dL
 - Any transfusion with overt bleeding
 - o Type 3b
 - Overt bleeding plus hemoglobin drop 5 g/dL or greater
 - Cardiac tamponade
 - Bleeding requiring surgical intervention for control (excluding dental/nasal/skin/hemorrhoid)
 - Bleeding requiring intravenous vasoactive agents
 - Type 4: VAD implantation-related bleeding (includes concomitant cardiac or non-cardiac surgical procedure)
 - Reoperation after the closure of incision or incisions used to implant the VAD to control bleeding
 - ≥ 50 kg: ≥ 4U pRBC within any 48 hours during the first 7 days postimplant
 - < 50 kg: ≥ 20 cm³/kg pRBC within any 24 hours during the first 7 days post-implant
 - Chest tube output > 2 liters within 24 hours
 - Type 5a: Probably fatal bleeding; no autopsy or imaging confirmation but clinically suspicious
 - Type 5b: Definite fatal bleeding; overt bleeding or autopsy or imaging confirmation
 - o For all types of bleeding, the event will be classified as:
 - Patient-related (e.g., coagulopathy unrelated to surgical technique such as non-adherence with anticoagulation medication resulting in inappropriately high level of anticoagulation, hepatic failure)
 - Management-related (e.g., related to surgical technique, hypertension, bleeding in the setting of inappropriate levels of anticoagulation)

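### The automatic pause triggers in section 17.2 do not name hemorrhagic stroke on apixaban, and some non-fatal ones count toward no trigger on either reading of Appendix B

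*Combined protocol and SAP*

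**What the plan says.** Section 17.2 lists three events in the apixaban arm that immediately pause enrollment for DSMB evaluation:

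- The clotting trigger is "≥ 2 thromboembolic events (ischemic stroke, arterial non-CNS embolism, device thrombosis, aortic root thrombus").
- The bleeding trigger, whose threshold is twice that of the other two, is "≥ 4 major bleeding events (Types 3-5").
- The death trigger, which depends on how the cause is classified, is "≥ 2 deaths due to either thromboembolic events or major bleeding events".

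Appendix B (19.2) supplies the definitions. Major bleeding means Types 3-5. Under the bleeding entry it adds that "CNS bleeding will be captured under cerebrovascular event/stroke", and it defines a cerebrovascular event as a stroke of either kind, ischemic or hemorrhagic. The protocol does not say whether a CNS bleed captured as stroke also receives a bleeding type.

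Section 17.1 gives the DSMB a wider remit: "The DSMB will review cumulative study data to evaluate safety, study conduct, scientific validity, and data integrity of the study". The DSMB charter is a separate document and is not available here.

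**The concern.** Hemorrhagic stroke belongs to the primary endpoint through its stroke component, and survival free of it is a secondary endpoint (12.1, 12.2). It is among the gravest bleeding harms of an anticoagulant, and every patient starts on aspirin as well (7.3). Section 10.1.4 expects less intracranial hemorrhage with DOACs than with warfarin, so events may be few, but the same section says the risks of apixaban in LVAD patients are unknown.

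An automatic pause rule should give the same answer whoever codes the event. Here two careful readers could disagree on whether a hemorrhagic stroke adds to the count. On either reading, some disabling but non-fatal events add to nothing.

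**Working it through.** **No figure to reproduce.** The protocol gives no operating characteristics for the pause rule and no event rates, and section 15.2 says the sample size was not statistically derived. The check is therefore a comparison of texts, followed by an illustration at assumed rates.

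**Step 1. Follow a hemorrhagic stroke through the triggers.**

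| Event on apixaban | Thromboembolic trigger | Bleeding trigger if CNS bleeds are not typed | Bleeding trigger if CNS bleeds are also typed |
|---|---|---|---|
| Non-fatal, managed medically, no transfusion, hemoglobin drop under 3 g/dL | No (ischemic only) | No | No (at most Type 2) |
| Non-fatal, with transfusion, surgical control or a hemoglobin drop of 3 g/dL or more | No | No | Yes (Type 3a or 3b) |
| Fatal | No | Unclear | Yes (Type 5a or 5b) |

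The third column takes the capture rule as removing CNS bleeding from the bleeding scale. The fourth takes it as saying only where the event is recorded. Types 3a and 3b include "Any transfusion with overt bleeding" and "Bleeding requiring surgical intervention for control (excluding dental/nasal/skin/hemorrhoid"), without excluding the CNS by name. Their other criteria are the hemoglobin drop, cardiac tamponade and intravenous vasoactive agents. Type 4 concerns implant-related bleeding. None of these is met simply because the bleed is intracranial, so the first row counts toward nothing on either reading. The death trigger follows the same logic: a fatal hemorrhagic stroke counts if it is accepted as major bleeding, which Type 5 permits but the text does not state.

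**Step 2. Inputs for the illustration.**

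- n = 20 apixaban patients (sections 7.3 and 14.1.8). Replacement patients would raise the number exposed.
- h = 24-week risk of hemorrhagic stroke: 1%, 2.5%, 5% (assumed).
- q = 24-week risk of other major bleeding: 5%, 10%, 20% (assumed).
- At most one counted event per patient; patients independent.

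**Step 3. Chance of reaching the four-event bleeding trigger.** With X the number of counted events,

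P(X ≥ 4) = 1 − Σ (k = 0 to 3) C(20, k) p^k (1 − p)^(20 − k),

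where p = q if no hemorrhagic strokes count and p = q + h if all do. For q = 0.10 with none counted: 1 − (0.1216 + 0.2702 + 0.2852 + 0.1901) = 0.133. For q = 0.10, h = 0.05, all counted, p = 0.15: 1 − (0.0388 + 0.1368 + 0.2293 + 0.2428) = 0.352.

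| q | None counted | All counted: h = 1% | h = 2.5% | h = 5% |
|---|---|---|---|---|
| 5% | 1.6% | 2.9% | 5.8% | 13.3% |
| 10% | 13.3% | 17.1% | 23.5% | 35.2% |
| 20% | 58.9% | 63.1% | 69.0% | 77.5% |

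At q = 10% the gap is 4, 10 or 22 percentage points.

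**Step 4. If half of the hemorrhagic strokes already count** (assumed), the starting point is p = q + h/2. At q = 10% this gives 15.1%, 18.1% or 23.5%. Counting all of them then adds 17.1 − 15.1 = 2.0, 23.5 − 18.1 = 5.4, or 35.2 − 23.5 = 11.7 points: about 2, 5 or 12.

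**The case against.** Four objections deserve weight.

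- **Other safeguards exist.** The DSMB reviews cumulative data, "The study may be terminated by the Sponsor at any time", non-exempt SAEs go to the IRB within 24 hours (14.1.8), and each patient's data are reviewed individually (15.2). The triggers pause enrollment only, and enrolled patients continue. This stands, and it limits the consequence. A reader might infer that hemorrhagic stroke goes unmonitored; the documents do not support that. None of these safeguards, however, settles how the automatic rule counts the event.
- **The charter may resolve it.** It may. But section 17.2 refers to the charter for termination criteria and sets out the pause triggers in the protocol itself, so the protocol text should be clear on its own.
- **Fatal events probably count.** A reader might infer that hemorrhagic strokes, fatal or not, count toward nothing. That goes too far: Types 5a and 5b have no site exclusion, and 5b accepts imaging confirmation, which suits a fatal intracranial bleed. For deaths the supportable word is unclear.
- **The chance of seeing an event overstates the effect.** With 20 patients the chance of at least one hemorrhagic stroke is 1 − (1 − h)^20 = 18%, 40% or 64% at the assumed risks. One event fires no event trigger, so these are not the size of the gap. Hemorrhagic strokes alone, with no other bleeding, would reach four with probability 0.004%, 0.14% or 1.6%. The change in P(X ≥ 4) is the relevant measure.

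**Conclusion.** The gap is real and should be fixed. Section 17.2 names hemorrhagic stroke in no trigger. Non-fatal events count toward none if CNS bleeding is not typed, and medically managed ones without a Type 3 feature count toward none even if it is. Fatal events could count, but the protocol leaves that unstated. This finding rests on the text and needs no event rate.

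Its size does depend on assumed rates. At 10% other major bleeding, counting every hemorrhagic stroke raises the chance of reaching the four-event trigger by at most 4, 10 or 22 points, or by about 2, 5 or 12 if half already count. The all-or-none gap is 1 to 12 points at 5% other bleeding and 4 to 19 points at 20%.

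A reader might also infer that the thromboembolic list in 14.1.8, which has stroke without a qualifier and omits aortic root thrombus, is an error to be aligned with 17.2. The documents do not support that. Section 14.1.8 governs an individual patient's drug, whereas 17.2 governs an enrollment pause, so a difference between the lists is not in itself a fault.

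**What to change.** Add to section 17.2 that any hemorrhagic stroke or intracranial hemorrhage in the apixaban arm counts as a major bleeding event for the four-event trigger, whether or not it meets a Type 3-5 criterion, and that a death from it counts in the two-death trigger. Check that the DSMB charter agrees.

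Leave the word stroke in 14.1.8 as it is. As written, any stroke on apixaban leads to conversion to warfarin, whereas a first bleeding event stops only aspirin. Narrowing the word to ischemic stroke would take hemorrhagic stroke out of the rule that stops apixaban. A first event would then be handled as bleeding with apixaban continued, or, if not coded as bleeding, be covered by no rule in that section.

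The cost is a short protocol amendment with IRB approval and a charter check; no new data are needed. The downside is a somewhat higher chance of a temporary enrollment pause, by the amounts in the working. Those are upper figures to the extent that some events already count.

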10.2 Estimated Enrollment Period

This study will randomize approximately 40 at one-center in the U.S. The anticipated enrollment period is approximately 12-24 months.

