12 OUTCOME DETERMINATIONS

12.1 Primary Endpoint

Freedom from death or hemocompatibility related adverse events (stroke, device thrombosis, bleeding, aortic root thrombus and arterial non-CNS thromboembolism) at 24-weeks.

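### The death trigger for the automatic enrollment pause leaves out apixaban-arm deaths of undetermined cause

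*Combined protocol and SAP*

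**What the plan says.** Section 17.2 introduces its list with "The following clinical events in the apixaban arm will result in an immediate pause of study enrollment for an evaluation by the independent DSMB". The list has three entries: two or more thromboembolic events of four named kinds, four or more major bleeds (Types 3-5), and "≥ 2 deaths due to either thromboembolic events or major bleeding events". Patients already enrolled carry on during a pause.

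The same section also provides that "The study may be terminated by the DSMB based on concerns for significant harm to study participants based on criteria outlined in the DSMB charter", and lets the sponsor terminate at any time. Section 17.1 has the DSMB review cumulative data. It gives no review interval and refers to a separate charter.

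The primary endpoint (12.1) is "Freedom from death or hemocompatibility related adverse events", with no restriction on cause of death. All-cause mortality is a secondary endpoint (12.2). Section 14.1.8 puts deaths of every cause on the adverse event eCRF. Appendix B defines bleeding Type 5a as "Probably fatal bleeding; no autopsy or imaging confirmation but clinically suspicious".

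**The concern.** The risk summary in section 10.1.4 says that the risks of apixaban in LVAD patients, device thrombosis and stroke above all, are not known. It adds that they are expected to resemble those seen in atrial fibrillation. In that setting, a sudden death that nobody can explain might be a clot or a bleed. As worded, the death trigger treats it as neither.

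What is at stake is the automatic step. A pause under 17.2 acts at once and does not wait for a scheduled review. If deaths accumulate without an assigned cause, the rule does not call for a pause, and new patients continue to be randomized to apixaban until someone acts by another route.

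**Working it through.** **1. Which deaths reach a trigger.**

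- Suspected fatal bleeding without autopsy or imaging is Type 5a, hence major bleeding. It counts toward the bleeding and death triggers.
- In Appendix B, suspected device thrombosis needs at least one sign (hemolysis, heart failure not explained by structural disease, or abnormal pump parameters) plus an accompanying event. Death is one of the accompanying events. So a death with one such sign can count as thromboembolic without autopsy.
- A death with a confirmed embolism, ischemic stroke, pump thrombus or aortic root thrombus counts.
- A death with none of these findings meets no trigger, and no number of such deaths does.

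The death trigger also adds little as it stands. Two deaths from the listed thromboembolic events already satisfy the first trigger. The third adds only two bleeding deaths, or one of each kind.

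**2. Is there a plan figure to reproduce?** No. The documents give no operating characteristics for the pause rule, and section 15.2 says the sample size was not statistically derived. What follows is illustration.

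**3. Inputs.** From the documents:
- 20 apixaban patients (sections 7.3 and 14.1.8; replacement could raise the number exposed)
- 40 patients randomized 1:1, and "The anticipated enrollment period is approximately 12-24 months"

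Assumed, because the documents do not give them:
- 24-week mortality q = 5-15%
- share of deaths undetermined u = 20-40%
- share attributed to clot or major bleeding a = 19-40%. The 19% borrows the share of LVAD deaths that section 5 ascribes to stroke.
- 3-6 months until the next DSMB review

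**4. Accrual while no pause operates.** 40/24 to 40/12 = 1.67 to 3.33 patients a month, half of them to apixaban: 0.83 to 1.67. Over 3 to 6 months: 0.83 × 3 = 2.5 up to 1.67 × 6 = 10 further apixaban patients.

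**5. Deaths the rule does not see.** Number of undetermined deaths ~ Binomial(20, q × u).
- Low: 0.05 × 0.20 = 0.01. P(≥1) = 1 − 0.99^20 = 18.2%; P(≥2) = 1.7%.
- High: 0.15 × 0.40 = 0.06. P(≥1) = 1 − 0.94^20 = 71.0%; P(≥2) = 34.0%.

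**6. Effect of counting them.** The present death trigger fires with probability P(Binomial(20, q × a) ≥ 2). The amended one fires with P(Binomial(20, q × (a + u)) ≥ 2), which includes pairs of one attributed and one undetermined death.

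| q | u | a | Present | Amended | Added (points) |
|---|---|---|---|---|---|
| 5% | 20% | 19% | 1.5% | 5.7% | 4.2 |
| 5% | 20% | 40% | 6.0% | 12.0% | 6.0 |
| 15% | 40% | 19% | 11.0% | 53.9% | 42.9 |
| 15% | 40% | 40% | 34.0% | 71.1% | 37.1 |

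The added probability therefore runs from about 4 to 43 percentage points. These figures cover the death trigger alone.

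**The case against.** **Deaths are already watched.** Section 14.1.8 sends serious adverse events to the IRB within 24 hours, whether or not they are thought drug-related. Death is a serious adverse event and is not among the exempt anticipated events. The DSMB reviews cumulative data, the sponsor can stop the trial, and the charter may contain an all-cause criterion or a rule for expedited death notices. All of this stands. It rules out the reading, which a reader might take from 17.2 alone, that unexplained deaths go unsupervised. None of the routes visible in the documents is an automatic pause, however, and the charter cannot be checked.

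**Who attributes the deaths.** Because the trial is open label, a reader might infer that unblinded investigators decide which deaths count, or that unexplained deaths usually cannot be attributed. The documents support neither inference. They do not say who assigns cause of death. The investigator assessment in section 14.1.5 concerns relation to study drug, a different question. They also give no data on how often cause can be established.

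**The rule is deliberately about hemocompatibility.** All three triggers target clotting and bleeding, and including death of any cause in a composite endpoint does not oblige a pause rule to do the same. That is fair. It is an argument against an all-cause trigger, not against counting deaths that may themselves have been clots or bleeds.

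**The upper figures are a worst corner.** They combine the highest assumed mortality with the highest undetermined share, and they include deaths after enrollment closes, when a pause protects no one. With uniform accrual over T months and 24 weeks (about 5.5 months) of follow-up at constant hazard, the share of follow-up before the last enrollment is 1 − 5.5/(2T): 77% for T = 12 and 88% for T = 24. The 34% for two or more undetermined deaths then falls to about 24-29%. This objection stands.

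**Conclusion.** The gap is in the text and does not depend on any rate. Apixaban-arm deaths without documented signs of bleeding or suspected device thrombosis are not counted, and two or more of them would not by themselves cause the automatic pause. It is a gap in one trigger, not an absence of oversight, and it is narrower than the trigger's wording first suggests because Type 5a and suspected device thrombosis bring in deaths with supporting signs.

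Its practical size is uncertain: about 2% to 34% for two or more uncounted deaths in 20 patients, wholly on assumed mortality and undetermined shares, with the upper end lower once only deaths during enrollment are considered. The case for the change is that it costs little and that all-cause deaths are already collected. It does not rest on a demonstrated high probability of harm.

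**What to change.** In 17.2, keep the number 2 and the other two triggers. Extend the third to deaths due to thromboembolic events or major bleeding events, *or of undetermined cause; a death counts unless another cause is documented*. Deaths with a documented other cause stay excluded. Align the DSMB charter with the wording or, if the charter already covers such deaths, bring 17.2 into line with it. State in either place who assigns cause of death.

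No new data collection is needed. The cost is more pauses: the death trigger would fire more often by about 4 to 43 percentage points under the assumptions above. Net added pauses would be fewer, because some of those trials would already have paused on the event triggers and some deaths fall after enrollment closes. Each pause prompts a DSMB evaluation.
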